9.2.4. Pharmacodynamic Assessments

Blood samples will be collected for measurement of lyso-Gb₃ levels in plasma. In addition, to get a better understanding of early PD biomarkers for Fabry disease, blood will be collected for exploratory cardiac biomarkers such as high sensitivity tropin and NT-proBRN. Plasma levels of lyso-Gb₃ will be measured using a validated LCMS assay.

9.2.5. Efficacy Assessments

9.2.5.1. Estimated Glomerular Filtration Rate

Estimated GFR will be calculated using the Schwartz formula according to the standards of the central laboratory.

9.2.5.2. Urine Protein and Albumin Levels

Protein and albumin (or microalbumin) levels in urine (as part of urinalysis) will be measured.

9.2.5.3. Echocardiogram

The key echocardiogram parameter considered for efficacy is LVMi. In addition, ejection fraction, fractional shortening, left ventricular internal diameter end diastole and end systole, midwall fractional shortening, and wall thickness will be assessed.

Echocardiograms will be read centrally.

9.2.5.4. Subject Questionnaires

All Questionnaires will be provided in a separate Patient Outcomes Manual.

9.2.5.4.1. Electronic Diary

Subjects will be asked to complete daily diary entries at approximately the same time of day (preferably in the evening before bed time) beginning on Day 1 and for the duration of the study. Diary entries will include completion of the FABPRO-GI and Pain Questionnaire for Clinical Trials (24-hour version).

The FABPRO-GI and Pain Questionnaire for Clinical Trials (24-hour version) consists of 4 questions regarding gastrointestinal signs and symptoms and 2 questions regarding pain relative to the past 24 hours. Subjects will record the frequency and consistency of stools using the Bristol Stool Scale, a pictorial chart and descriptive text for 7 types of stool, ranging from Type 1 (separate hard lumps, like nuts – hard to pass) through Type 7 (watery, no solid pieces – entirely liquid). Subjects will also rate the severity of their worst occurrence of diarrhea, constipation, tummy pain, and overall pain from 0 (none) to 10 (worst possible); for tummy pain, subjects will indicate the location of any tummy pain using a diagram.

9.2.5.4.2. Patient Global Impression of Change

The PGI-C consists of 4 questions regarding diarrhea, abdominal pain, overall pain, and daily living to be answered using a 7-point scale. Subjects will complete the questions by themselves without assistance from their parents or legal guardians.

9.2.5.4.3. Fabry-Specific Pediatric Health and Pain Questionnaire

The FPHPQ includes questions about Fabry disease-specific symptoms (eg, sweating, pain, dizziness and tiredness, heat and cold intolerance, swollen eyelids, gastrointestinal symptoms, feeling thirsty, difficulty hearing, ringing or buzzing noise in the ears, and ability and enjoyment to participate in sports). The frequency of these symptoms will be rated using a 5-point Likert scale (always, often, sometimes, seldom, never). Pain intensity is measured on a 10-point scale, numeric responses are given for onset of pain and school days missed, and yes/no questions are posed about difficulty hearing and other problems not specifically mentioned. There are 2 age-specific self-report versions for children 8 to 12 years and 13 to 18 years, respectively.

9.2.5.4.4. Pediatric Quality of Life Inventory

The PedsQL^{$^{\text{TM}}$} is a modular approach to measuring health-related quality of life in healthy children and adolescents and those with acute and chronic health conditions. It consists of 23 items and includes questions about physical functioning, emotional functioning, social functioning, and school functioning relative to the prior 7 days, using a 5-point scale. Both parents or legally-authorized representatives and subjects complete the appropriate version of the PedsQL independently of one another. Parents or legally-authorized representatives and subjects may self-administer the questions after introductory instructions are given by study site personnel.

10. ADVERSE EVENTS AND SERIOUS ADVERSE EVENTS

Investigators and study site personnel are responsible for detecting, documenting, and reporting AEs and SAEs. For each subject, reporting of AEs and SAEs begins after written informed consent is provided.

10.1. Definitions

10.1.1. Adverse Event

An AE is defined as any untoward medical occurrence in a subject or clinical investigation subject administered a pharmaceutical product and which does not necessarily have a causal relationship with this treatment. An AE can therefore be any unfavorable and unintended sign, symptom, or disease temporally associated with the use of a medicinal product, whether or not considered related to the medicinal product.

Therefore, AEs include the following:

- the onset of new signs, symptoms, conditions, and illnesses
- exacerbation of pre-existing conditions or illnesses
- abnormal laboratory findings deemed clinically significant by the investigator
- physical examination changes deemed clinically significant by the investigator
- abnormal medical evaluation findings (eg, ECG) that are not documented at screening and/or, in the investigator's opinion, represent a clinically significant change in the subject's health during study participation

Note: Screening medical evaluation findings (eg, ECG) that were not previously provided as medical history and can be determined as starting before screening, are not considered AEs and will be recorded as medical history.

Adverse events will be recorded in the eCRF and subject's source record beginning from the time written consent (assent) is provided through the follow-up visit (at least 30 days after the last dose of study drug).

A single diagnosis should be entered when known. If a clear diagnosis cannot be determined at the time of eCRF completion and the subject's source record entry, each sign and symptom must be recorded individually, until a final diagnosis is established. Conditions, signs, symptoms, etc that are present in the subjects' medical history at screening should only be reported as AEs if they worsen (ie, increase in severity) since screening.

Adverse events that begin after the first dose of study drug will be considered treatment-emergent adverse events (TEAEs).

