5.3.2.2. Safety

Migalastat has a favorable safety profile in adults based on results from a comprehensive development program. A total of 386 adult and adolescent (\geq 16 years of age) subjects have been exposed to migalastat in Phase 1, Phase 2, and Phase 3 clinical studies conducted globally. The extent of exposure to migalastat among subjects with Fabry disease in Phase 2 and Phase 3 studies is approximately 595.2 patient-years, with the longest subject exposure being 11.2 years as of 17 March 2017.

No treatment-related deaths have been reported in clinical studies, and most serious adverse events (SAEs) were not considered treatment-related. In Phase 1 studies, the most frequently reported adverse event (AE) was headache. In completed Phase 2 studies in subjects with Fabry disease (Study FAB-CL-201 through Study FAB-CL-204), the most frequently reported AEs were headache, arthralgia, diarrhea, and nausea. In completed Phase 3 studies in subjects with Fabry disease (Study AT1001-011, Study AT1001-012, and Study AT1001-041), the most frequently reported AEs were diarrhea, headache, arthralgia, pain in extremity, nausea, fatigue, nasopharyngitis, dizziness, and influenza, though the order by frequency was not necessarily the same in all 3 studies.

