8.2.1. Inclusion Criteria

Subjects must meet all of the following criteria to be considered for enrollment in the study:

- 1. have a parent or legally-authorized representative who is willing and able to provide written informed consent and authorization for use and disclosure of personal health information or research-related health information, and subject provides assent, if applicable provides written informed consent
- 2. male or female, diagnosed with Fabry disease aged between 12 and < 18 years at baseline, and who might benefit from specific treatment for their condition, in the opinion of the investigator
- 3. confirmed, amenable *GLA* variant determined using the migalastat amenability assay

Note: For subjects without a known amenable *GLA* variant, *GLA* genotyping must be performed prior to Visit 2.

Note: For subjects with a *GLA* variant that has not yet been tested in the Migalastat Amenability Assay, amenability testing must be completed before Visit 2.

- 4. weight of \geq 45 kg (99 pounds) at screening
- 5. treatment-naïve or discontinued ERT treatment at least 14 days prior to screening
- 6. have at least one complication (ie, historical or current laboratory abnormality and/or sign/symptom) of Fabry disease, for example:
 - a. corneal whorls
 - b. neuropathic pain and/or acroparesthesia and/or acute crises persisting or recurring at least twice over the previous 3 months or longer, or; requiring management with analgesia
 - c. Fabry disease-related gastrointestinal signs and symptoms (eg, diarrhea, abdominal pain) persisting or recurring at least twice over the previous 3 months or longer
 - d. hypohidrosis (present for at least 3 months)
 - e. LVMi above the normal range for age and sex

- f. rhythm and/or conduction disturbances, for example:
 - episode of tachycardia or bradycardia,
 - arrhythmia, or;
 - abnormal PR, QRS, or QT interval
- g. reduced eGFR (using the Schwartz formula) for age and sex, or hyperfiltration (> 135 ml/min/1.73 m²)
- h. proteinuria or albuminuria in spot urine (early morning preferable) or as determined by the investigator (based on local laboratory results documented in the patient's medical record)
- i. plasma lyso-Gb₃ levels above normal (based on local laboratory results documented in the patient's medical record)
- j. hearing impairment and/or tinnitus
- 7. able to swallow capsules

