10.1.2. Serious Adverse Event

An SAE is any AE occurring at any dose that results in any of the following outcomes:

- death
- a life-threatening event
 - This includes any AE that in the view of either the investigator or sponsor places the subject at immediate risk of death. It does not include an AE that, had it occurred in a more serious form, might have caused death.
- requires inpatient hospitalization or prolongs existing hospitalization
 - Hospitalization signifies the subject has been admitted, regardless of duration, for observation and/or treatment that would not have been appropriate in a physician's office or outpatient setting.
 - Hospitalizations for elective or pre-planned treatment of a pre-existing condition do not have to be reported as SAEs if the following criteria are met:
 - the condition is documented in the subject's medical history and has not worsened since the informed consent form was first signed; and
 - the condition and planned procedure are documented in the subject's source records at screening.
 - Emergency room/department or outpatient treatments that do not result in admission do not have to be reported as an SAE, unless another SAE criterion is met. Events assessed and treated in these circumstances should be captured as AEs in the eCRF and documented in the subject's source records.
 - Hospitalizations solely based on subject logistics (eg, subject is admitted due to limited hospital accessibility for what would otherwise be an out-subject procedure) do not have to be reported as SAEs provided that the hospitalizations are clearly defined as such in the subject's source record.
- persistent or significant incapacity or substantial disruption of the ability to conduct normal life functions
- congenital anomaly/birth defect

An important medical event that does not result in one of the above serious outcomes may be considered an SAE when, based upon appropriate medical judgment, it may jeopardize the subject and may require medical or surgical intervention to prevent one of the listed serious outcomes. Examples of such medical events include allergic bronchospasm requiring intensive treatment in an emergency room or at home, blood dyscrasias, or convulsions that do not result in inpatient hospitalization, or development of drug dependency or drug abuse.

If the following 4 elements are known, the event must be reported as described in Section 10.4.2:

- identifiable subject
- event term
- study drug

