10.3. Severity Assessment

The investigator or a qualified sub-investigator will review each event and use the following definitions for rating intensity:

- Mild: awareness of sign, symptom or event, but the AE is easily tolerated and does not interfere with daily activity
- Moderate: discomfort enough to cause interference with usual activity and may warrant intervention, but the subject is still able to function
- Severe: incapacitating with inability to do usual activities or significantly affects clinical status, and requires medical intervention

It is important to distinguish the difference between events that meet the definition of serious and events that are deemed as severe in intensity. Adverse events assessed as severe in intensity are not SAEs unless at least 1 of the definitions in Section 10.1.2 is met. Adverse events of any intensity must be reported as SAEs if at least 1 definition in Section 10.1.2 is met.

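### Protocol Section 10.1.1 is inconsistent on worsened pre-existing conditions: any exacerbation is an AE, yet reporting is limited to increased severity, so more frequent or longer Fabry symptoms at the same grade may go unreported

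*Protocol*

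**What the plan says.** Protocol Section 10.1.1 gives two statements on worsened pre-existing conditions. Its list of what counts as an AE includes "exacerbation of pre-existing conditions or illnesses", with no qualifier. Further down, the recording instruction says that conditions, signs and symptoms in the medical history at screening "should only be reported as AEs if they worsen (ie, increase in severity) since screening". The same section makes an AE treatment-emergent if it begins after the first dose.

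Protocol Section 10.3 has three grades, defined by how far an event interferes with activity. Moderate, for example, is "discomfort enough to cause interference with usual activity and may warrant intervention, but the subject is still able to function". Neither frequency nor duration appears in any grade.

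Protocol Section 8.2.1 defines two of the qualifying Fabry complications largely by persistence or recurrence. Criterion 6b covers neuropathic pain, acroparesthesia or "acute crises persisting or recurring at least twice over the previous 3 months or longer", and also admits pain that needs analgesia. Criterion 6c applies the same persistence-or-recurrence test to GI symptoms.

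SAP Section 11.2 tabulates reported TEAEs. The tables by system organ class (SOC) and preferred term (PT) count each subject once. The overall summary adds the number of events and a rate, total events over total patient-years of exposure. The SAP has no rule of its own for worsened pre-existing conditions.

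**The concern.** Safety is a primary objective of both stages and there is no control arm, so the AE tables must stand largely on their own. The symptoms most exposed to the restrictive sentence are also those in which a drug effect and the disease are hardest to separate. According to Protocol Section 5.3.2.2, in completed Phase 3 studies "the most frequently reported AEs were diarrhea, headache, arthralgia, pain in extremity, nausea, fatigue", among others. Diarrhea and pain are also Fabry symptoms by this protocol's own account (Sections 5.1 and 5.4, criteria 6b and 6c).

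If a site follows the restrictive sentence, a subject whose crises or diarrhea come more often on treatment, each at the usual grade, produces no AE record. If another site follows the exacerbation item, the same change is an AE. The result is inconsistent reporting between sites. Relative to the section's own exacerbation criterion, any resulting error in the TEAE tables is an under-count. The Data Monitoring Committee, which reviews summaries of safety data, would be affected in the same way.

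**Working it through.** No figure in the plan is in dispute, so the check is a comparison of texts followed by a count of the subjects who could be affected.

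**1. Path from a symptom change to a table.** The change must first be reported as an AE (Protocol 10.1.1), then have begun after the first dose to be a TEAE (10.1.1), and is then counted in SAP 11.2. No step derives an AE from the diary or a questionnaire. A change not reported at the first step is absent from the TEAE tables.

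**2. Test case.** A subject enters under 6b with recurrent moderate pain crises. On treatment they become more frequent or longer, each still moderate.

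- Exacerbation item in 10.1.1: an AE.
- Reporting sentence in 10.1.1: not an AE, because severity has not increased.
- Section 10.1.2, if a crisis is treated in an emergency room or as an outpatient without admission: "Events assessed and treated in these circumstances should be captured as AEs in the eCRF".
- Section 10.3: reportable if the greater burden lifts the grade. From moderate, that means a severe event, which is incapacitating or significantly affects clinical status and requires medical intervention.

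The first two lines give opposite answers. The last two capture some cases, depending on where the subject is treated or how the site grades.

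**3. Which outputs move.** Assume 20 subjects who all complete 12 months of 30 days, and a year of 365.25 days.

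- SOC and PT tables: one subject whose only event under a term is not reported changes that percentage by 1/20 = 5 percentage points. Further recurrences in a subject already counted change nothing.
- Overall rate: exposure is 20 × 360 / 365.25 = 19.7 patient-years, so each unreported event lowers the rate by 1 / 19.7 = 0.051 per patient-year.

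**4. How many subjects the rule could touch.** Inputs are about 20 subjects (Protocol 8.1) and the registry figures in Protocol 5.4: neuropathic pain in 58.8% of boys and 40.5% of girls, GI symptoms in 18% of children. The sex split is not fixed, so the range is shown.

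- Pain history, all girls: 20 × 0.405 = 8.1
- Pain history, all boys: 20 × 0.588 = 11.8
- Pain history, assumed 10 and 10: 10 × 0.588 + 10 × 0.405 = 9.9
- GI history: 20 × 0.18 = 3.6

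**5. Whether the other instruments fill the gap.** The FPHPQ rates symptom frequency at baseline and at Months 1, 3, 6, 9 and 12, and the SAP summarises its change from baseline (8.3.3), but as efficacy in the intent-to-treat population. The diary starts on Day 1 with no pre-dose run-in. Its listed summaries are monthly averages of pain scores and of diarrhea and constipation severity; stool frequency is recorded but is not among them (SAP 8.3.1).

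**The case against.** The strongest reply is that the protocol already captures much of this. The exacerbation item is unqualified, emergency and outpatient treatment has its own capture instruction, and an activity-based grade can rise when symptoms become frequent or long enough to disrupt daily life. The FPHPQ measures frequency against baseline, the Patient Global Impression of Change tabulates worsened status for diarrhea, abdominal pain and overall pain, and concomitant medication use is itself a safety endpoint. The eCRF Completion Guidelines, cited in Section 10.4.1 but not available here, may also address the point.

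This stands to a degree. A reader might infer that more frequent symptoms can never reach the safety tables; the routes above show that some will. What remains is that those routes depend on site interpretation, treatment setting or regrading, and the questionnaires do not feed the AE tables.

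It could also be argued that the second sentence merely defines exacerbation, so there is no contradiction. On that reading frequency and duration are simply excluded, and the same wording needs attention.

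Other stronger inferences are not supported:

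- That a history already graded severe can never worsen. The documents do not say that medical history is graded; SAP 7.3 summarises it by SOC and PT. The supportable point is that no usual frequency or intensity is stated as the comparator for a change since screening.
- That headache and nausea are suppressed in the same way. Both are listed as AEs, but the documents do not name them as Fabry symptoms, so without such a history they are ordinary new events.
- That TEAE incidence is the primary endpoint. Safety is a primary objective, but no safety endpoint is labelled primary.

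**Conclusion.** The point holds as an inconsistency within Protocol Section 10.1.1 that the SAP does not resolve. Followed literally, the reporting sentence allows Fabry pain or GI symptoms that become more frequent or longer at an unchanged grade to go unreported, so TEAE incidence and the event rate can be under-counted and can differ by site.

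About 8 to 12 of 20 subjects with a pain history and about 4 with a GI history could come under the rule. This assumes that registry prevalence applies to the sample; inclusion criterion 6, which requires at least one complication, could make it higher. A reader might take these counts as missed events, or multiply them by an assumed rise in episodes. The documents give no basis for either: they contain no rate of symptom change on treatment and no way to tell how many changes would escape the other routes. The size of any under-count is therefore unknown.

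**What to change.** Reconcile the two sentences in Section 10.1.1 by changing the parenthesis to read: ie, increase in severity, frequency or duration, or change in character, compared with pre-dose status. Align the sentence's closing reference to screening with that comparator for events after the first dose, and carry the wording into the eCRF Completion Guidelines.

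For subjects not yet dosed, record the usual frequency and intensity of ongoing Fabry symptoms at baseline. For subjects already dosed this cannot be collected prospectively. Use their baseline FPHPQ frequency items as the comparator, and add to the SAP a summary of shifts in those items in the safety population. If data collection is too advanced to amend the protocol, add the shift summary and state the limitation in the clinical study report.

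The costs are more AE records, some of which will be disease fluctuation, and a slightly less favourable TEAE incidence. The wording change needs a formal amendment (Protocol 14.3). SAP Section 13 reports the Stage 1 interim safety analysis as already done, so earlier data would remain under the old wording; the report should say when the wording changed.

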7. INVESTIGATIONAL PLAN

7.1. Study Design

This is a Phase 3b, 2-stage, open-label, uncontrolled, multicenter study to evaluate the safety, pharmacokinetics, pharmacodynamics, and efficacy of migalastat treatment in pediatric subjects 12 to < 18 years of age and weighing \ge 45 kg (99 pounds) with Fabry disease and with amenable *GLA* variants. Subjects must be either naïve to enzyme replacement therapy (ERT) or have stopped ERT at least 14 days at the time of screening.

The study will consist of 2 stages. Stage 1 will be a treatment period of approximately 1 month (4 weeks); Stage 2 will be a treatment period of 11 months and a 30-day (untreated) safety follow-up period. There will be no break in treatment between Stages 1 and 2. Prior to Stage 1, there will be a screening period lasting at least 14 days and up to 30 days (or more, if *GLA* genotyping is required). Stage 1 and 2 together will consist of a 12-month treatment period, and a 30-day safety follow-up period, for a total of approximately 14 months. Subjects may have the option to enroll in a long-term extension study conducted under a separate protocol.

At screening, all subjects first must have a blood test to confirm their *GLA* variant prior to completing any additional screening assessments. Subjects with a documented variant (ie, those who have a full genotype report) that is known to be amenable to migalastat may continue to be screened according to the procedures outlined for Visit 1.

For subjects without a known *GLA* variant, screening will resume after receipt of the variant result, if amenability is confirmed. For subjects with a *GLA* variant that has not yet been tested in the Migalastat Amenability Assay, amenability testing also will be performed. If variants are determined to be amenable according to the Migalastat Amenability Assay, screening procedures will resume at that time. If the variant is non-amenable, the subject will be considered a screen failure. (Note: the Migalastat Amenability Assay may take up to 8 weeks.)

The study design is displayed in Figure 1.

Figure 1: Study Design

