- identifiable reporter

Additionally, the investigator's assessment of an event's relationship to study drug (see Section 10.2) is essential for the sponsor to appropriately process the report and must be included.

Subjects and parents or legally-authorized representatives must be informed and understand that they should report events meeting the definition for SAE to study site personnel as soon as possible (and not wait until their next study visit).

If a non-serious event becomes serious, the change in status must be appropriately entered in the eCRF and the subject's source record, and reported to the sponsor as described in Section 10.4.2.

If the investigator becomes aware of an SAE that occurs more than 30 days after the last dose of study drug, and considers the event possibly, probably, or definitely related to study drug, the investigator should contact the Medical Monitor (see Table 1)/Clinical Operations Lead to determine how the SAE should be documented and reported.

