6.7. Handling of Missing Data

6.7.1. Missing Start and Stop Dates for Adverse Events

For AEs, partially missing start dates will be imputed for the purpose of determining treatment emergence only.

Partially missing start dates will be imputed as follows:

For a missing day,

- If the month and year are equal to the month and year of the date of the first dose of study drug, then the date of the first dose of study drug will be used.
- Otherwise, the first day of the month will be used.

For a missing day and month,

- If the year is equal to the year of the first dose of study drug, then the date of the first dose of study drug will be used.
- Otherwise, the first day of the month and the first month of the year will be used.

If the stop date is not missing and the imputed start date is after the stop date, then the stop date will be used.

If the start date is completely missing and the stop date is on or after the date of first dose of study drug, the AE will be considered a TEAE.

If both the start date and stop date are missing, the AE will be considered a TEAE.

Missing stop dates for adverse events will not be imputed.

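### The TEAE definition turns on onset alone, so an adverse event that starts between consent and first dose and then worsens or becomes serious on drug can fall outside the TEAE tables.

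*Protocol*

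**What the plan says.** Protocol 10.1.1 holds the only definition of treatment emergence in either document: "Adverse events that begin after the first dose of study drug will be considered treatment-emergent adverse events (TEAEs". SAP 11.2 builds its tables on the term without defining it, and SAP 14 declares no departure from the protocol's analyses, so the protocol sentence governs.

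Collection begins earlier than treatment. Protocol 10 states that "reporting of AEs and SAEs begins after written informed consent is provided". Protocol 7.1 states that, before Stage 1, "there will be a screening period lasting at least 14 days and up to 30 days", or more where genotyping is required.

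On worsening, Protocol 10.1.1 counts "exacerbation of pre-existing conditions or illnesses" as adverse events and says that conditions in the medical history at screening "should only be reported as AEs if they worsen (ie, increase in severity) since screening". On seriousness, Protocol 10.1.2 says: "If a non-serious event becomes serious, the change in status must be appropriately entered in the eCRF". It also requires the event to be reported to the sponsor. It is silent on the onset date and on opening a new record.

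On dates, SAP 6.7.1 says: "For AEs, partially missing start dates will be imputed for the purpose of determining treatment emergence only". Where the known part of the date matches the first dose, "then the date of the first dose of study drug will be used". An event with no start date that ended on or after the first-dose date is a TEAE, and so is an event with neither date.

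The endpoint in Protocol 11.1.1 and SAP 3.2.3 has three parts: TEAEs, SAEs, and adverse events that lead to stopping study drug. The last two are not limited to treatment-emergent events.

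**The concern.** Evaluating safety is a primary objective of both stages, and TEAE incidence is in the first-listed safety endpoint. A usual treatment-emergent definition also counts events present before dosing that get worse afterwards. This one does not.

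The pre-dose window is not trivial. It lasts at least two weeks, and subjects may have stopped enzyme replacement as little as 14 days before screening. Symptoms that appear in screening and worsen on drug are therefore plausible, and they are among the events a safety study needs to show. Leaving them out can only lower the counts.

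**Working it through.** There is no stated figure to reproduce, because the point concerns an event definition. The check has three steps.

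**1. Which onsets count.** The SAP 6.7.1 start-date rules were applied with an arbitrary first-dose date of 10 March 2019, under two date-level readings of the protocol's word *after*.

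| Start date recorded | Date used | Onset date > first dose | Onset date ≥ first dose |
|---|---|---|---|
| 25 Feb 2019 (screening) | 25 Feb 2019 | not TEAE | not TEAE |
| 10 Mar 2019 (Day 1) | 10 Mar 2019 | not TEAE | TEAE |
| Mar 2019, day missing | 10 Mar 2019 (imputed) | not TEAE | TEAE |
| 2019, day and month missing | 10 Mar 2019 (imputed) | not TEAE | TEAE |
| 11 Mar 2019 (Day 2) | 11 Mar 2019 | TEAE | TEAE |

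The first row carries the point. A screening onset is not a TEAE under either reading, so the gap does not depend on how *after* is programmed.

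**2. What happens when such an event worsens.** Take an event with onset on 25 February that becomes more severe, or serious, after 10 March.

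- The explicit re-reporting rule in Protocol 10.1.1 applies to conditions in the medical history at screening. This event began after consent.
- If it turns serious, Protocol 10.1.2 asks for the status change to be entered. If the site updates the existing record, the onset stays at 25 February.
- The record is then outside the SAP 11.2 tables by SOC and PT, by intensity and for serious TEAEs, and outside the overview rows for TEAEs leading to discontinuation and to death.
- The discontinuation row does not match its endpoint: the endpoint refers to adverse events, the row to TEAEs.
- The SAEs row sits inside an overview headed as a summary of TEAEs, so its scope is unclear.

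**3. Scale.** The planned size is about 20 (Protocol 8.1). One subject is 1/20 = 5 percentage points. Exact (Clopper-Pearson) 95% intervals, for scale only:

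- 0/20 = 0% (0 to 16.8%)
- 1/20 = 5.0% (0.1 to 24.9%)
- 2/20 = 10.0% (1.2 to 31.7%)

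The shift applies only to a subject with no other event in the same table row.

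**The case against.** The strongest reply is that the protocol already provides a route. Exacerbation of a pre-existing condition is an adverse event in its own right, and that bullet is not limited to medical history. An exacerbation that begins on drug could be entered with a post-dose onset and so be a TEAE. Inclusion criterion 6 requires at least one Fabry complication, so many relevant symptoms will be medical history, where the worsening rule is explicit. Protocol 10.4.1 leaves recording details to eCRF Completion Guidelines that are not part of these documents and may already ask for a new record. Nor do serious events disappear: the protocol plans summaries of deaths and SAEs, the SAP lists subjects with SAEs, all data are listed, and the DMC reviews all available safety data. The study is descriptive, and no test turns on the count.

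Most of this stands, and it rules out the reading that nothing captures worsening on drug, or that events which become serious vanish. It does not close the gap. The exacerbation bullet does not say whether further worsening of an adverse event that is already open needs a new record, and neither document makes worsening part of treatment emergence.

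A reader might also infer that events on Day 1 drop out and that the word *after* cancels the SAP's imputation. The documents do not support that. The protocol says after the dose, not after its date, so a post-dose event on Day 1 qualifies. SAP 6.7.1 imputes to the first-dose date solely to decide treatment emergence and uses an on-or-after rule when the start date is missing. Both imply that the first-dose date counts. What remains is that this rule is never stated outright for Day 1 events without a recorded time.

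**Conclusion.** The point holds in a limited form. The definition rests on onset alone, and an adverse event that starts between consent and first dose and worsens or becomes serious under the same record is outside the SAP 11.2 TEAE tables. The error runs one way, towards under-counting, in part of a primary safety outcome.

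Its size is 5 percentage points per affected subject in a given table row, assuming 20 subjects and no other event for that subject in the row. The documents give neither a rate of adverse events in screening nor a chance that they worsen, so no expected number of missed events can be given. The conclusion also assumes that sites update the existing record rather than open a new one, which the documents leave open. The gap is narrow but cheap to close, and it should be closed.

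**What to change.** In Protocol 10.1.1 and SAP 11.2, define a TEAE as an adverse event with onset on or after the first dose, or one with earlier onset that increases in severity or becomes serious on or after the first dose. Instruct sites to record the worsening as a new adverse event entry with its own date.

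For consistency with SAP 6.7.1, also state that events dated or imputed to the first-dose date count as treatment-emergent unless a recorded time shows onset before the dose.

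The cost is one definition in each document and one eCRF completion instruction. The protocol change would go through the amendment procedure in Protocol 14.3. SAP 13 reports that Stage 1 data have already been analysed, so existing records with pre-dose onset should be checked for a later increase in severity or seriousness. The downside is that slightly more events are counted.
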